A lumbar catheter and two IVs will be placed in the evening, with the goal of placement between 20:00-21:00, for collecting 6 ml of CSF every 2 hours for 36 hours (Figure 5) and 6ml of blood according to the specimen schedule (pg 7 of protocol). In order to efficiently use each participant's samples, each individual will also receive a placebo medication (for Specific Aim 2) and an infusion of ¹³C₆-leucine on Day 1 starting after catheter placement 0 (t=0) to label protein *in vivo* during intracellular translation in order to monitor A β kinetics (17, 40, 47). Participants will be allowed to sleep as they are able after receiving study medication (placebo or suvorexant). Nursing staff will use dim red lights (safelights) when collecting CSF and blood in the dark. The lumbar catheter ports will be placed on the outside of the gown sleeve for easy access to minimize disturbance during fluid collection. Participants will then sleep until final awakening in the morning.

During Day 2, all participants will be in well-lit rooms with regular monitoring for staying awake and naps will not be permitted. At 21:00 on Day 2 (t=24), all participants will follow the same sleep routine except that there will be no infusion of labeled ¹³C₆-leucine. All participants will again receive placebo for the second night. The IVs and lumbar catheters will be removed following the last CSF collection (t=36). Afterwards, participants will be monitored at the Clinical Research until discharge at approximately 17:00. A β kinetics will be quantified by mass spectrometry (MS).

Aim 2: To determine the effect of pharmacologic sleep induction on CNS A β kinetics in individuals with poor sleep efficiency

45 participants with sleep efficiency <85% measured by actigraphy will be admitted to the CRU in the afternoon (Day 1). All participants will have their sleep monitored with PSG throughout the study as described in Aim 1. A lumbar catheter and two IVs will be placed in the evening, with the goal of placement between 20:00-21:00, for collecting 6 ml of CSF and 6 ml of blood according to the specimen schedule (pg 7 of protocol). Following catheter placement on Day 1 (t=0), all participants will start an infusion of labeled ¹³C₆-leucine to label proteins *in vivo* during intracellular translation in order to monitor A β kinetics (17, 40, 47).

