Assignment to a study group: Participants with good sleep efficiency will not be randomized but will be placed in the “good sleep efficiency” group for Aim 1 and receive placebo. Participants with poor sleep efficiency will be randomized to receive their placebo (Aim 1) or suvorexant (Aim 2) at the research unit admission. The 45 participants in the poor sleep efficiency group will be randomized to receive placebo (15 participants) or suvorexant 10 or 20 mg (30 participants). 15 participants will receive 10 mg of suvorexant for two nights and 15 participants will receive 20 mg of suvorexant for two nights. In addition to being a FDA approved drug for the treatment of insomnia, suvorexant is also a drug with the same mechanism of action as was used in experiments to decrease A β with sleep in mice, therefore this will be a direct translation of this finding. FDA approved doses range from 5-20 mg. The drug’s mechanism of action is to block orexin-A and orexin-B receptors. The orexin neuropeptide acts in the brain to promote wakefulness. Through antagonism of this system, sleep is induced. In a phase IIb randomized, double-blind, placebo-controlled study of patients with primary insomnia, suvorexant 10 mg increased sleep efficiency from 65.1% at baseline to 82.9% at night 1 and 84.4% at one month. Placebo-treated subjects increased sleep efficiency from 65.9% at baseline to 76.8% at night 1 and 77.8% at one month [Ref. 48].

Collaborating sites: None

B. Sources of Materials

Specimens, records, or data: We will obtain the following from our participants (de-identified)

- Cerebrospinal fluid (CSF) specimens: Each participant regardless of study aim or group will have an indwelling lumbar catheter placed for the collection of CSF every 2 hours for 36 hours (hours 0, 2, 4, 6, 8, 10, 12, 14, 16, 18, 20, 22, 24, 26, 28, 30, 32, 34, 36). At each time point, 6 ml of CSF will be collected. At the end of the study an additional 2 ml of CSF (when available) will be sent to the lab to check for any signs of infection.

Therefore, a total of 116 ml of CSF will be collected from each participant over 36 hours. It is expected that the catheter will fail to draw CSF during the study for some participants. This will result in missing CSF samples and missing CSF safety labs.

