Access to individually identifiable private information about human subjects: The only individually identifiable private information about human subjects are name, date of birth, phone number, mailing address, email, and social security number (latter only for participant reimbursement). These are stored separately from the rest of the data, which are labeled with a random number code only. Only team members trained in the protocol and are approved by the Human Research Protection Office (HRPO) will have access to private identifiable information, including the Principal Investigator, research coordinator/polysomnographic technicians, and the mentor.

C. Potential risks

Lumbar Catheter

1. Discomfort during the procedure is common and mild. Some people may have discomfort sitting in the same position for the duration of the lumbar catheter placement. Lidocaine will be used for local anesthesia, which feels like a small pinch followed by

burning sensation (<10 seconds). There is pressure but not pain during the insertion of the lumbar puncture needle. During the lumbar catheter procedure, participants may experience momentary (<1 second) cramping or pain in a leg, due to the needle or the catheter briefly touching a floating nerve ending.

2. Back soreness is common and mild. Some people have soreness of the area where the needle and catheter were inserted, especially when the lidocaine wears off. This soreness resolves by itself over 2-3 days.
3. Feeling faint is common and mild. As with any medical procedure, some people feel faint. This is a normal response and is *not* a physical effect of the needle.
4. Post-lumbar catheter headache occurs frequently (50-80% of participants) and is mild to moderate. Another possible symptom is ringing in the ears. Individuals may have a headache following placement of a lumbar catheter, due to the decreased volume of CSF. For the majority of individuals, the headache resolves when the catheter is removed. Occasionally (30% or less), this headache persists after removal of the catheter and requires treatment with a “blood patch.”
5. Bleeding is extremely rare, but is moderate to severe when it occurs. In individuals with problems of blood clotting, a lumbar catheter may cause a large amount of bleeding.
6. Infection is an extremely rare risk of a lumbar catheter and can be moderate-to-severe. Very rarely, the lumbar puncture needle and catheter may introduce pathogens internally, leading to infection.

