1. Discomfort during the procedure: To minimize discomfort, participants will sit at the edge of the bed with supports and pillows to keep them in an ergonomic position. Lidocaine will be used for local anesthesia. Only physicians experienced in performing lumbar catheters will perform this procedure.
2. Back soreness: Participants are provided with information sheets on using heat, stretching, and acetaminophen if back soreness occurs.
3. Feeling faint: If a participant feels faint, s/he will be assisted in lying down in the bed until the feeling has passed. The lumbar catheter can be performed with participants lying down on their side, in this case.
4. Post-lumbar catheter headache: This risk will be minimized by having the participants lie in bed with their heads down (the Trendelenburg position) for one hour after the catheter is removed. Participants will remain in bed for 6-8 hours after the catheter is removed. Participants are also informed they can minimize this risk by having caffeine after the lumbar catheter is removed, and drinking plenty of water throughout the study while the catheter is in place. If a post-lumbar catheter headache does occur, participants will be offered treatment with a “blood patch.”
5. Bleeding: Individuals with this risk (blood clotting problems or taking anticoagulants) are excluded from participation in the study.
6. Infection: Proper sterile technique will be used during all lumbar catheter placements. At the end of the study immediately prior to the removal of the catheter, an additional 2 ml of CSF will be drawn, when available, and sent to the lab to check for any signs of infection. Further, participants are given a 24/7 phone number for a member of the research team after discharge from the Clinical Research Unit in case of complications.

Intravenous catheter

1. Discomfort during the procedure: Only physicians and nurses experienced in placing intravenous catheters will perform the procedure.
2. Bruising at phlebotomy site: Discomfort from bruising can be alleviated by moist heat pack, which can be provided in the Clinical Research Unit.
3. Feeling faint: If a participant feels faint, s/he will be assisted in lying down in the bed until the feeling has passed. Participants will be encouraged to drink plenty of water during the study, to minimize the chance of feeling faint.

Suvorexant

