Protections for research involving vulnerable populations: This project does not involve vulnerable populations.

Plan for adverse events: Response to an adverse event or risk will differ based on the type and severity of the event. A Data Safety Monitoring Committee (DSMC) will serve to mitigate these risks and ensure a formal process for dealing with adverse events.

- *Data Safety Monitoring Committee:* A DSMC consisting of experts in the study procedures and the effects of sleep disorders on cardiac and psychiatric morbidities has been established for the proposed study.
 - Qualified individuals monitoring the study: The DSMC members have substantial experience and expertise in this area of research and in clinical research, and are qualified to monitor the study.
 - The DSMC will meet prior to enrollment of any participants, to review study procedures and potential adverse events, and then provide guidance on HRPO application and consent/informational materials.
- *Web-Based Instruction on Conducting Human Research:* In accordance with the NIH policy effective October 1, 2000, this is to certify that Washington University key personnel involved in the design and conduct of the human subjects research aspect of this proposal have been educated on the protection of human research participants. An interactive web-based program that provides information on conducting human research and the informed consent process is organized into five modules. These modules include detailed information, examples and exercises related to basic principles, history, consent form process, and after approval requirements such as continuing review and adverse events.
- *Review of adverse events:* All personnel who will be in contact with participants and/or data are prepared to identify adverse events and have been instructed to report their occurrence immediately to the principal investigator.
- *Definition:* An adverse event will be defined as any negative change in health related to study-related procedures.
- *Classification of Events:* A Safety Documentation form will assess for details of any adverse events, severity, and relatedness to study procedures.
- *Data Collection Procedures for Adverse Events:* At each visit and with each interaction/phone call, adverse events will be screened for and recorded. If any adverse events have occurred, these will be logged in the Safety Documentation form.

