- *Reporting Procedures:* The Safety Documentation form will be discussed during the DSMC meetings. The DSMC will meet according to participant completion goals (after 15, 23, 30, 38, and 45 participants complete the study). If a serious adverse event occurs, the DSMC will meet as soon as possible to determine the course of action. If the DSMC deems changes to the study are necessary for safety reasons, the study will halt immediately until the changes have been approved through the Washington University HRPO.

- *Criteria for stopping the study:* Circumstances that would warrant stopping the study are not anticipated. However, should any circumstances arise that compromise the safety of the participants, they will be reported to the DSMC who will suspend research until appropriate safeguards allow continuation of the study.
- *Adverse Event Reporting Period:* There will not be a set end-date for reporting adverse events.
 - Expected adverse events (*i.e.* are listed above and on consent forms) will be discussed at DSMC meetings. Also, they will be reported to the HRPO during annual renewals.
 - Unexpected serious adverse events will be reported within 10 days, per HRPO requirements.

The only anticipated adverse events that would require medical intervention are:

1. A post-lumbar catheter headache that does not resolve with conservative measures such as rest, hydration, and caffeine intake. This will be treated with “blood patch” in the Clinical Research Unit, at no cost to the participant.
2. Side effects to suvorexant such as somnolence and confusion upon waking. Risks from suvorexant are minimized with the inclusion/exclusion criteria and that participants will only receive the drug for 2 nights in the monitored setting of the Clinical Research Unit at Washington University. If any severe adverse events occur on suvorexant, then the drug will be discontinued and the participant monitored closely.

3. Potential Benefits of the Proposed Research to Human Subjects and Others

Potential benefits to participants

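### After discharge, adverse events are captured only if the participant phones in, although back soreness and plausibly some headaches outlast the stay

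*Combined protocol and SAP*

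**What the plan says.** **Timing.** The Experiment section (Aims 1 and 2) aims for catheter placement between 20:00 and 21:00 on Day 1. It removes the catheter after the last CSF draw at t=36 and discharges the participant at about 17:00 that day. The Aim 1 text fixes the clock: "At 21:00 on Day 2 (t=24), all participants will follow the same sleep routine".

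**Named risks.** Under Potential risks, Lumbar Catheter:
- Back soreness is common and mild: "This soreness resolves by itself over 2-3 days".
- Headache affects 50-80% of participants and for most ends when the catheter comes out, but "Occasionally (30% or less), this headache persists after removal of the catheter and requires treatment" with a blood patch.
- Infection is called extremely rare. No rate and no time of onset are given.

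**After discharge.** Protections Against Risk, Lumbar catheter, item 6 says "participants are given a 24/7 phone number for a member of the research team after discharge from the Clinical Research Unit". The Data and Safety Monitoring Plan adds round-the-clock access to study staff and physicians.

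**How adverse events are collected.** Under Plan for adverse events: "At each visit and with each interaction/phone call, adverse events will be screened for and recorded". Events go on the Safety Documentation form, which the Data Safety Monitoring Committee (DSMC) discusses. Reporting has no fixed end date.

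**Infection check.** A final 2 ml CSF sample is taken when available. Sources of Materials expects catheter failure in some participants: "This will result in missing CSF samples and missing CSF safety labs".

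**Blood patch.** Protections Against Risk, item 4: "If a post-lumbar catheter headache does occur, participants will be offered treatment" with a patch. Plan for adverse events ties the patch to "A post-lumbar catheter headache that does not resolve with conservative measures such as rest, hydration, and caffeine intake".

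**The concern.** The screening rule works only when there is a visit or a call. The supplied text schedules neither after the participant leaves the unit, and the sleep diary and actigraphy also stop on the day of discharge. From then on, an event is recorded only if the participant chooses to ring. An open-ended reporting period means a late report will be accepted, but it does not cause anyone to ask.

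This matters because at least one common risk has a stated duration longer than the remaining stay. The protocol defines an adverse event as a negative change in health related to study procedures, so soreness and headache at home both count. If nobody phones, they will be missing from the form the DSMC reviews, and the recorded frequency and duration of catheter complications will be too low by an unknown amount. Some participants will also leave without a CSF safety result, and the text describes no step for them beyond the general phone line.

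**Working it through.** **Inputs.** t=24 is 21:00 on Day 2; placement goal 20:00-21:00 on Day 1; removal at t=36; discharge about 17:00 on Day 3 (Experiment, Aims 1 and 2). Soreness 2-3 days, any headache 50-80%, persistent headache 30% or less (Potential risks). 60 completers (Human Subjects Involvement, Characteristics, and Design).

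**1. Removal to discharge.**
- t=0 at 21:00 on Day 1: 21:00 + 36 h = 09:00 on Day 3, and 17:00 - 09:00 = 8 h.
- t=0 at 20:00: removal is at 08:00, and 17:00 - 08:00 = 9 h.

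The 6-8 hours of bed rest that the protocol sets after removal fit this interval.

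**2. Placement to discharge.** 36 + 8 = 44 h, or 36 + 9 = 45 h. This is the time in the unit during which catheter complications can be observed directly.

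**3. Soreness past discharge.** Two to three days is 48-72 h. The protocol does not say when the period starts, so both readings are shown as assumptions.
- From insertion: 48 - 45 = 3 h to 72 - 44 = 28 h after discharge.
- From removal: 48 - 9 = 39 h to 72 - 8 = 64 h after discharge.

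Soreness that lasts the stated 2-3 days outlasts the stay on either reading.

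**4. Headache.**
- Any headache: 0.50 x 60 = 30 to 0.80 x 60 = 48 participants.
- Persisting after removal, if the 30% applies to everyone: at most 0.30 x 60 = 18.
- If it applies only to those with headache: at most 0.30 x 30 = 9 to 0.30 x 48 = 14.4, so about 9-14.

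The protocol does not state the denominator. The 30% is an upper limit and is timed from removal. The chance of at least one such headache among 60 is 1 - (1 - p)^60. It exceeds 99.9% for p between 15% and 30% and is still 95% at an assumed p of 5%. How many would remain after discharge, 8-9 h later, cannot be computed from the documents.

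**5. Infection.** With no rate and no onset time, there is nothing to compute.

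**6. Blood-patch wording.** Read literally, item 4 under Protections Against Risk applies to any post-catheter headache. Potential risks reserves the patch for headache that persists after removal. Plan for adverse events reserves it for headache that conservative measures do not resolve. These are different triggers.

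**The case against.** The strongest reply is that the period of greatest risk is spent in the unit. Headache can begin once the catheter is placed, and participants are under 24-hour nursing for about 44-45 h from placement to discharge. Afterwards they have a number to call at any hour, information sheets on soreness, and blood patches given in the Clinical Research Unit at no cost. A headache treated by the study would therefore be known to the team, and what is most likely to be missed is mild and self-limiting. Consent and contact pages are also not in the supplied text, so a follow-up call described there cannot be excluded. None of this touches the amyloid-beta outcomes.

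Most of that stands, and it limits the size of the point. It does not supply a planned moment after discharge at which anyone asks.

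Four stronger readings are tempting, but the documents do not support them:
- **That up to 30% go home with headache.** The figure is an upper limit, timed from catheter removal, with no stated base. Persistence past discharge is plausible, since the protocol foresees headache that conservative measures do not resolve, but no share is given.
- **That infection is shown to arise after discharge.** No onset time is stated. The phone line is merely listed under the infection item.
- **That headache is watched for only 8 hours, or that participants have no contact.** Observation runs from placement, and the phone line exists. What is missing is scheduled contact.
- **That the blood-patch rules cover 30-48 participants against 18.** The passages can be read as one loosely worded sequence of conservative measures and then a patch. The count of 18 would also borrow the 30% for a passage that gives no rate. What remains is a wording conflict.

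**Conclusion.** The point holds in a limited form. As written, safety capture after discharge is participant-initiated, and the rule for screening adverse events has no planned trigger once the participant leaves, 8-9 h after catheter removal. Back soreness of the stated duration outlasts the stay by about 3-28 h (from insertion) or 39-64 h (from removal). Some of the headaches that persist after removal, at most 18 of 60 or 9-14 depending on the base, plausibly do so as well.

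The consequence is under-recording of home events in what the DSMC sees. Its extent is unknown, and it is likeliest for milder events. The conclusion assumes that no follow-up contact is described in material not supplied, and that catheter placement meets its target window. It is a worthwhile, inexpensive improvement to safety capture and does not affect the efficacy analysis. The blood-patch wording is a separate, smaller inconsistency.

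**What to change.** In the data collection procedures under Plan for adverse events, add at least one scheduled, scripted adverse-event telephone contact by the existing team, placed after the 2-3 day soreness window and logged on the Safety Documentation form. Record on the same form whether the CSF safety result was reviewed or is missing. Whether further contacts are needed, and when, is for the investigator and the DSMC to decide.

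The cost is about 60 short calls (one for each of 60 participants) and a few lines of protocol text, with no new procedure. If such calls are already made in practice, only the wording is needed.

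Separately, reconcile the blood-patch statements in Potential risks, Protections Against Risk (item 4) and Plan for adverse events so that they give one trigger. Which trigger applies is a clinical decision that this review does not make.

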Statistical Analysis and Power Calculation: All participants will be screened to determine if they have good or poor sleep efficiency as described above. 15 participants with good sleep efficiency will be treated with placebo (Aim 1). 45 participants with poor sleep efficiency will be randomized to either placebo (N=15) (Aim 1) or suvorexant 10 mg (N=15) or suvorexant 20 mg (N=15) (Aim 2). Change in CNS A β 40 and A β 42 production, clearance, and concentration in placebo-treated participants with poor sleep efficiency will be compared to placebo-treated participants with good sleep efficiency (Aim 1) and individuals with poor sleep efficiency treated with suvorexant (Aim 2) using a repeated measures analysis of variance (RM ANOVA), or repeated measures analysis of covariance (RM ANOCOVA) when covariates such as age are included in the analysis (49). Correction for multiple comparisons will be performed. A main question is whether the production rate of CSF A β during the production phase differs between subjects with good or poor sleep efficiency, or treated with drug, that will be statistically tested by appropriate interactions between subjects groups and time in the RM ANOCOVA. The average concentration of CSF A β over the entire time course during the sleep period will be tested by the main effects of subjects' groups, adjusting for the possible effects of age. Other parametric mixed effects models incorporating the typical sinusoidal profile over time will also be considered in the analyses. These analyses will be implemented by PROC MIXED/SAS or SPSS (50).

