This study is a clinical trial, however it is not an NIH-defined phase III clinical trial. Suvorexant is already FDA-approved for the treatment of insomnia. This study will use suvorexant under the FDA-approved indication. Comparisons are being made between poorly-sleeping treated (suvorexant) and untreated individuals (placebo). There is a Data Safety Monitoring Committee and monitoring plan as described in section “*2.B Protections Against Risk*” above. [name]., [name]., [name]., and [name]. will monitor the study for adverse events, adherence to the protocol, inclusion/exclusion criteria, and accrual/withdrawal rates. All serious adverse events will be reported to the Washington University HRPO: a) death – immediately; b) life threatening with 7 calendar days; c) all other SAEs within 15 calendar days using the HRPO Reportable Event Form (SAE report). Should there be an adverse event that occurs that increases the risks to the participants, the following steps will be taken: suspension of the study until risks are re-evaluated and discussed with the HRPO. Other reports that will be generated are yearly summary reports. These will be sent to the HRPO annually.

Given that the study requires significant involvement from the participants, we have taken steps to make the study less taxing for participants. These steps include having nurses available in the CRU for assisting the research participants at all times and providing 24 hour/7 day/week access to study staff and physicians.

All participants will be identified by a deidentified study number to protect patient confidentiality. Participants may be linked to the “sleep quality” study in Epic if they already have a record in the Epic system. Spreadsheets listing the participants’ name and corresponding study number will be managed by the study coordinator, and will be stored in a password protected file behind the Neurology firewall. Only the research team will have access to this spreadsheet. Data monitoring and analysis will be performed by the principle investigator. Data will also be collected on any adverse events related to the study procedures.

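### The adverse event definition requires relatedness to procedures before an event counts, conflicts with the form that grades relatedness afterwards, and does not name the study drug, so unrelated non-serious events may go unlogged

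*Combined protocol and SAP*

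**What the plan says.** Five statements bear on what is logged. The first three are under Plan for adverse events in section 2.B; the last two are in section 5, Data and Safety Monitoring Plan.

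- What counts as an event is fixed first: "An adverse event will be defined as any negative change in health related to study-related procedures". Relatedness is thus a condition of entry.
- The item on classifying events comes next and describes what is graded: "A Safety Documentation form will assess for details of any adverse events, severity, and relatedness to study procedures". Here relatedness is an attribute of an event that has already been identified.
- On how events are found, the plan is broad: "At each visit and with each interaction/phone call, adverse events will be screened for and recorded". Anything found is then entered on the same form.
- Section 5, on scope: "Data will also be collected on any adverse events related to the study procedures".
- Section 5, on serious events: "All serious adverse events will be reported to the Washington University HRPO". That sentence sets no relatedness condition.

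Reporting Procedures makes the Safety Documentation form the material discussed at DSMC meetings. Later in the same plan, the list of anticipated adverse events that would need medical intervention includes "Side effects to suvorexant such as somnolence and confusion upon waking".

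**The concern.** An adverse event is usually recorded first and attributed second. Here the definition reverses that order: staff must judge an event related before it qualifies for the form. Whatever they judge unrelated can drop out before anyone sees counts by arm.

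The order matters in this study because section 1.C, Potential risks, gives competing explanations for the same symptoms. Headache is listed under the lumbar catheter (50-80% of participants) and under suvorexant. Dizziness is listed under bed rest and under suvorexant. Next-day tiredness is listed under polysomnography and next-day drowsiness under suvorexant. Attribution in a single participant is therefore weak evidence, and a pattern across arms would be more informative. That pattern is visible only if events are logged before causality is judged, and if the form asks about the drug as well as the procedures.

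**Working it through.** The point rests on wording, and the plan states no figure to reproduce. The check sets the statements side by side.

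**1. Definition against classification.** Suppose the definition governs. Then every event on the form is already related to procedures, and the relatedness item can at most grade how strongly. Suppose instead that the form is meant to separate related from unrelated events. Then unrelated events must be allowed onto it, and the definition and the section 5 sentence on scope are wrong. The protocol does not say which reading governs. The restriction appears in two separate sections, so it is not a single slip.

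**2. Whether the collection rule settles it.** Screening at every contact is broad, but what is screened for is adverse events, so the rule inherits the definition. It fixes how often staff ask, not what counts.

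**3. Drug against procedures.** The definition, the relatedness item and the section 5 sentence on scope all refer to procedures. The list of anticipated events includes suvorexant side effects, so the protocol clearly intends these to count. As described, however, the form has no item asking about relatedness to suvorexant. A headache ascribed to the catheter would be logged, but a possible link to the drug would not be recorded.

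**4. Which events are exposed.** Take cough or diarrhea in a suvorexant participant that staff attribute to a coincidental illness. Both are listed as suvorexant reactions in section 1.C. Under the literal definition the event is unrelated to procedures and need not be logged.

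**5. Who is affected.** The suvorexant arms hold 15 + 15 = 30 participants, the randomised placebo arm 15, and the non-randomised good sleepers 15, for a total of 60. The definition applies to all of them. Any descriptive summary of drug against placebo concerns the 45 randomised.

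**6. Form of the distortion.** Let p be the true event rate in an arm and c the share of events that pass the relatedness call. The recorded rate is p × c.

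| Assumed p, both arms | c, suvorexant | c, placebo | Recorded, suvorexant | Recorded, placebo |
|---|---|---|---|---|
| 0.20 | 0.5 | 0.5 | 0.20 × 0.5 = 0.10 | 0.20 × 0.5 = 0.10 |
| 0.20 | 0.9 | 0.5 | 0.20 × 0.9 = 0.18 | 0.20 × 0.5 = 0.10 |

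All p and c values are assumptions that show direction only. An equal c in both arms loses events without creating a difference. An unequal c creates one where none exists. The documents supply neither p nor c, so no size can be attached.

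**The case against.** The strongest reply is that the plan, taken as a whole, captures more than the definition suggests. A relatedness item makes most sense if events can be entered before the question is settled, and it could be graded by degree. Personnel must report adverse events to the principal investigator at once, and events are asked about at each contact. Serious events go to the HRPO without a stated relatedness condition and trigger a DSMC meeting. Expected events are to be discussed at DSMC meetings, and cough and diarrhea are on the expected list.

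Much of this stands. A reader might infer that unrelated events are never recorded; the form's relatedness item and the screening at each contact do not support that. A reader might also infer that a planned safety comparison of suvorexant with placebo is biased. The documents plan no such comparison: Statistical Analysis and Power Calculation covers amyloid-beta production, clearance and concentration only. Nor do suvorexant side effects fall outside the protocol's notion of an adverse event, since it lists them as such. Events blamed on the research-unit stay are arguably procedure-related, because admission, bed rest and polysomnography are part of the study. Coincidental illness is therefore the cleaner example.

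The conflict itself remains. The reporting duty, the screening and the discussion of expected events all concern adverse events, and so depend on the definition. The serious-event rule does not help with non-serious events.

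A practical objection is that collecting every negative health change could be open-ended. The protocol sets no end date for adverse event reporting, and study procedures could be taken to begin with the two weeks of home actigraphy. That is fair, and the fix must bound the window.

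**Conclusion.** The concern holds as an internal conflict with a practical consequence. Relatedness is built into what counts as an adverse event in two places, while the form grades it afterwards, and the study drug is missing from both the definition and the relatedness item. Under the literal rule, non-serious events judged unrelated may go unlogged. DSMC review and any descriptive safety summary by arm could then reflect a causality call made beforehand.

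This rests on staff applying the definition as written; if they follow the form instead, the loss may be small. Capture could differ by arm, but nothing in the documents shows that it would. The amyloid-beta analyses and the sample size are unaffected. The change is worth making because it is cheap and unlogged events may not be recoverable later.

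**What to change.** - **Definition (section 2.B).** Define an adverse event as any negative change in health within a stated collection window, whether or not considered related. State the start point, and state an end for unrelated events. The existing open-ended period can remain for related events.
- **Safety Documentation form.** Keep severity and relatedness as graded fields. Record relatedness separately for study drug and for study procedures.
- **Section 5.** Reword the sentence on data collection to match the new definition.

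The cost is two sentences, one additional form field and some additional minor events to log. Bounding the window keeps that extra logging limited.
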